5.4.3 Adverse Events

The survey period for AEs will be from the initiation of study treatment to before the initiation of administration in the extension study or until the end of follow-up.

Events that occurred after study drug administration until before the initiation of administration in the extension study or until the end of follow-up will be recorded as AEs. Concurrent diseases that worsened during the study will also be recorded as AEs. AEs that occurred after the subject has completed the study plan or has been discharged from the hospital or the study center will not be recorded.

AEs that have not resolved before the initiation of administration in the extension study or at the end of follow-up must be followed-up until resolved or judged to be no longer clinically significant or until they become chronic to the extent that they can be fully characterized. If the event resolves during the study period, the date of resolution is to be entered in the eCRF.

- CONFIDENTIAL -

See Appendix 4 “Liver Safety Monitoring and Assessment” for the assessment of AEs caused by DILI.

Herpes zoster should be entered as an AE information in the eCRF, and also, a separate Herpes Zoster (shingles) Worksheet should be prepared, and a copy should be submitted to the sponsor. If the sponsor considers necessary and requests for submission of forms for the purpose of providing additional information on other AEs, a form must be prepared to report to the sponsor.

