5.5 Adverse Events and Other Safety Aspects

5.5.1 Definition of Adverse Events (AEs)

An AE is defined as any untoward medical occurrence in a subject administered a study drug or has undergone study procedures and which does not necessarily have a causal relationship with this treatment. An AE can therefore be any unintended sign (including an abnormal laboratory finding), symptom, or disease temporally associated with the use of a medicinal (investigational) product, whether or not related to the medicinal (investigational) product.

An abnormality identified during a medical test (e.g., laboratory parameter, vital sign, ECG data, physical examination) should be defined as an AE only if the abnormality meets one of the following criteria:

- Induces clinical signs or symptoms
- Requires active intervention
- Requires suspension, interruption, or discontinuation of the study drug
- The abnormality or laboratory test value is clinically significant based on the opinion of the investigator or other responsible personnel

The particulars to be noted with respect to the AE are the name of the event, date of onset, date of disappearance, severity (at peak time), seriousness, treatment of the study drug, other treatment, outcome, causal relationship to the study drug, and rationale for the assessment of causal relationship. The rationale for the assessment of the causal relationship does not need to be recorded for all AEs but only at the request of the sponsor. The severity of each event should be recorded on a scale of Grade 1 to Grade 5 in the eCRF, and the causal relationship to the study drug should be recorded as "Probable," "Possible," or "Not related" (see Section

- CONFIDENTIAL -

5.5.3 Criteria for Causal Relationship to the Study Drug and Section 5.5.4 Criteria for Defining the Severity of an Adverse Event). The treatment of the AE (whether it was treated with pharmacotherapy or by other means) and the treatment of the study drug should be recorded in the medical record or other source documents and in the eCRF. The outcome should be recorded in the medical record or other source documents and in the eCRF as “resolved,” “alleviated,” “unresolved,” “resolved but with late effects,” “death,” or “unknown.”

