## 6.2 Safety Variables

- AEs
- Vital signs (body temperature, pulse rate and blood pressure in sitting position)
- Body weight
- Central ECG
- 12-lead ECG
- Central electrocardiogram
- Chest radiography
- Laboratory assessments

**Treatment emergent adverse events** (TEAEs) will be defined as any adverse event that started or worsened in severity after initial dose of study drug through Week52 or Withdrawal.

AE for the subjects who switched ASP015K 100 mg or ASP150 mg from Placebo at Week 12 or Week 28 will be handled as follows.

- AE onset before the first dose of week12 study drug will be considered to be occurred at Placebo.
- AE onset after the first dose of week12 study drug before the first dose of week28 study drug will be considered to be occurred at Placebo if the subject did not switch Placebo at Week 12. Else, if the subject switched ASP015K 100 mg or 150 mg at Week12, then the AE onset after the first dose of week12 study drug before the first dose of week28 study drug will be considered to be occurred at ASP015K 100 mg or 150 mg.
- AE onset after the first dose of week28 study drug will be considered to be occurred at ASP015K 100 mg or 150 mg, which is switched treatment from Placebo.

A drug-related TEAE is defined as any TEAE with possible, probable or missing relationship to study drug as assessed by the investigator. Moreover, any TEAE with missing relationship to study drug or reference drug was counted as drug related (probable).

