### 7.5.1 Adverse Events

If an AE occurs on the same date as the initial dose date, the subject will be asked to select one of the following (see the eCRF page for AE): onset before initial dose of study drug,

onset after initial dose of study drug. Any AEs occurring after initial dose of study drug through the follow-up period will be considered treatment emergent.

Adverse events will be coded using the Medical Dictionary for Regulatory Activities (MedDRA).

All adverse events reported during the study period will be presented in subject listings.

Only TEAEs in the study period will be analyzed, and 2 types of analyses will be performed: TEAE occurrence analysis and TEAE per 100 patient-years analysis, as described below. TEAE occurrence analysis will be displayed by whole treatment period and by the following period. Primarily, TEAE occurrence analysis for Week 0 to Week 12 will be conducted in the view of comparison with placebo.

TEAE occurrence analysis for overall treatment period will be conducted in focus for ASP015K dose groups.

1. Week 0 to Week 12
2. Week 12 to Week 28
3. Week 28 to Week 52 or Later

TEAE per 100 patient-years analysis will be displayed above category, and by Week 0 to Week 12, and overall period.

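### An adverse event that begins on placebo and becomes severe or serious after the switch to ASP015K is counted at its worst level under placebo

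*SAP*

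**What the plan says.** **Attribution.** SAP 6.2 assigns the events of placebo switchers by onset relative to a dose. For the first period: "AE onset before the first dose of week12 study drug will be considered to be occurred at Placebo". For Weeks 12–28, an event "will be considered to be occurred at Placebo if the subject did not switch Placebo at Week 12". Nothing is said about an event that spans a switch.

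**Definition.** The same section defines a treatment-emergent event as "any adverse event that started or worsened in severity after initial dose of study drug through Week52 or Withdrawal".

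**Recording.** Protocol 5.5.1 lists what is collected per event, including "date of onset, date of disappearance, severity (at peak time), seriousness", followed by a single outcome that may be death. No date of worsening is in the list. Protocol 5.4.3 turns worsening into an event in one case: "Concurrent diseases that worsened during the study will also be recorded as AEs".

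**Reporting.** SAP 7.5.1 names the main comparison: "Primarily, TEAE occurrence analysis for Week 0 to Week 12 will be conducted in the view of comparison with placebo". SAP Appendix 3 (Tables 16 and 17) tabulates serious, Grade 3 or higher, special-interest, discontinuation and death rows for placebo against 100 mg and 150 mg over that period.

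**The concern.** The onset date decides which treatment an event belongs to, but its grade, seriousness and outcome may have been reached later, on a different treatment. In the placebo arm, every patient still in the study has moved to ASP015K by Week 28, and inadequate responders move at Week 12. Harm reached on ASP015K can therefore be charged to placebo even when every date is complete and correct.

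At stake is the reading of the Week 0–12 safety tables, the main comparison with placebo. Serious infection matters most: Protocol 1.4 singles it out as a risk of this drug class, and SAP Appendix 8 defines it as an infection event regarded as serious, without asking when it became serious.

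**Working it through.** The plan gives no figure on this point, so there is none to reproduce. The check sets the rules side by side and then shows scale.

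**1. Can worsening after the switch create a new event?** Three possible routes, all in the text available:
- The worsening clause in the treatment-emergent definition is anchored to the initial dose. For these patients that dose is placebo, so the clause does not restart at the switch.
- Protocol 5.4.3 covers concurrent diseases. Protocol 5.2.2 defines these as conditions not cured when study treatment starts, so an event that began on placebo is not one.
- Protocol 5.5.1 asks for severity at its peak, which points to one record carried to its worst grade.

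None creates a new record.

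**2. Where does the event go?** Take an infection that starts in Week 11 on placebo, with a switch at Week 12, and becomes serious in Week 14 on ASP015K.
- Onset precedes the first Week 12 dose, so SAP 6.2 assigns it to placebo.
- Its one seriousness flag is positive, so it counts in the Week 0–12 placebo column for serious events and for serious infections, and in the Week 0–12 patient-year table.
- The Week 12–28 tables have columns for placebo patients who switched, but this event is deemed to have occurred on placebo and does not enter them.
- The overall tables show only 100 mg and 150 mg, so it is not there either.

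An event with onset in Weeks 12–28 on continued placebo that worsens after the Week 28 dose follows the same path into the Week 12–28 placebo column.

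**3. Is this how the SAP treats other safety data?** No. SAP 7.11.5 takes the laboratory minimum and maximum up to Week 12 from values before the first Week 12 dose, and uses the last value before ASP015K for switchers at the early visits. Severity, seriousness and outcome of adverse events have no such cut.

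**4. Do the active arms behave the same way?** They also carry peaks reached after Week 12 into the Week 0–12 column. There, the event moves between periods of the same drug. Only for placebo switchers does it move between treatments.

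**5. Scale.** Planned group size is 170 (SAP 4). Each affected patient not already counted in a row adds 1/170 = 0.59 percentage points to the placebo rate in that row.

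Illustration, assuming the Phase IIb (RAJ1) serious-event rates in Protocol 1.3 carry over: placebo 1.8% × 170 = 3.06, about 3 patients; 100 mg 5.5% × 170 = 9.35, about 9 patients.

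| Misplaced events k | Placebo | Difference (9 − 3 − k)/170 |
|---|---|---|
| 0 | 3/170 | 3.5 points |
| 1 | 4/170 | 2.9 points |
| 2 | 5/170 | 2.4 points |
| 3 | 6/170 | 1.8 points |

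The 100 mg rate is the highest of the RAJ1 groups (150 mg had no serious events), so the table shows sensitivity and is not a forecast. The documents give no value for k.

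**The case against.** Attribution by onset is a common convention. All events are listed, so a careful reader could find the cases. Every Week 0–12 column can be read consistently as onset in that period at the worst grade ever reached. Most RAJ1 events were Grade 1 or 2, and the problem needs an event that is ongoing at the switch and then worsens. Protocol 5.5.6 (follow-up of adverse events) appears in the contents but not in the text available. That section or the eCRF instructions may tell sites to open a new record on worsening. All of this stands, and it limits the size and certainty of the point. It does not remove the mechanism: a consistent column label does not make an event on ASP015K a placebo event.

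Several stronger readings are tempting but not supported:
- *An expected count.* A reader might assume a share of events ongoing at the switch and a share that worsen, and apply both to all placebo patients with an event. The documents give neither share. Only inadequate responders switch at Week 12, and dropouts never switch (in RAJ1, 17.9% of placebo patients stopped because of events). A count of severe or serious events also cannot be set against an expected count of serious events alone.
- *Week 0–12 as the only placebo comparison.* Tables 16 and 17 also show a placebo column for Weeks 12–28, although that group is selected by response.
- *A treatment-emergent definition that the data cannot support.* Its worsening clause refers to the initial dose, and Protocol 5.4.3 supplies the data for that.
- *Deaths certainly booked to placebo.* The overview death row does not say whether onset or date of death decides the period.
- *Events on the switch day as unassignable.* The SAP rule refers to the dose, and Protocol 5.1.1 places visit-day dosing after assessments, so findings from the pre-dose sample come before it.

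**Conclusion.** The point holds as a gap in the attribution rule. On the text available, an event that starts on placebo and becomes Grade 3 or higher or serious after the switch is reported at its worst level under placebo and under no ASP015K column. For switchers the direction is fixed: the placebo rate can only rise, and harm on ASP015K can only be understated. The number of such events is unknown, probably small and possibly zero. At about 0.6 points per patient, a few would matter only for rare outcomes such as serious events.

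The conclusion assumes that no rule in Protocol 5.5.6 or the eCRF instructions opens a new record on worsening, and that period columns follow onset as SAP 6.2 implies. A reader should not infer that the Week 0–12 comparison is known to be materially wrong.

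**What to change.** Amend the SAP as follows.

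1. **Listing.** List every adverse event ongoing at the first Week 12 or Week 28 dose, with its grade, its seriousness and, where source or SAE data give it, the date on which the worst grade or seriousness was reached. The documents do not show whether the SAE form carries that date, so the listing must allow for it to be unknown.
2. **Sensitivity tables.** Repeat the Grade 3 or higher, serious, special-interest and death rows with the same cut in all arms. An event known to have reached that level before the Week 12 (or Week 28) dose stays in the earlier period. One that reached it later, or at an unknown date while ongoing at that dose, goes to the next period under the treatment then taken. Label the result a worst-case bound where the date is unknown. Table 17 shows special-interest rows only for Week 0–12 and overall, so this version needs later-period columns for the switched groups.
3. **Death row.** State which date decides its period and treatment.

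Two shortcuts should be avoided. Moving every event ongoing at the switch to ASP015K would also move those already severe or serious on placebo. Cutting placebo alone at the switch would leave later peaks in the active arms and bias the comparison against ASP015K.

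The cost is one listing, one extra table version and a few lines of SAP text. The SAP is dated 18 January 2018 and the planned study period ends that month, so the fix does not depend on changing data collection.

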### 6.3 Pharmacokinetic Variables

Refer to PK analysis plan.

### 6.4 Pharmacodynamic Variables

- Change from baseline in MMP-3 level
- Change from baseline in vascular endothelial growth factor (VEGF) level
- Change from baseline for following variables in lymphocyte subset assays
- CD3+/Lymphocytes (%), CD3 (cells/uL)
- CD8+/Lymphocytes (%), CD8 (cells/uL)
- CD4+/Lymphocytes (%), CD4 (cells/uL)
- CD19+/Lymphocytes (%), CD19 (cells/uL)
- CD4/CD8 Ratio
- (CD16 or CD56)+/Lymphocytes (%), CD16 or CD56 (cells/uL)
- (CD16+ and CD56+)/CD3- (%), CD16+ and CD56+ (cells/uL)
- (CD16- and CD56+)/CD3- (%), CD16- and CD56+ (cells/uL)
- (CD16+ and CD56-)/CD3- (%), CD16+ and CD56- (cells/uL)
- (CD16- and CD56-)/CD3- (%), CD16- and CD56- (cells/uL)
- CD56 bright/CD3- (%), CD56 bright (cells/uL)
- CD56 dim/CD3- (%), CD56 dim (cells/uL)

### 6.5 Other Variables

- Duration of RA (years), calculated as: (Date of Baseline mTSS taken – Onset Date of RA +1) / 365.25, and then rounded to one decimal place. The onset date of RA doesn't have the day (e.g., 2013-03), therefore the first day of the month will be used (2013-03-01).  
\*: Missing onset date of RA will be imputed. For example, if month is missing (e.g., 2013), then the first day of January will be used (2013-01-01).

- Age at onset of RA (years), calculated as: (date of onset of RA – date of birth +1) / 365.25. Onset Date of RA will be handled in the same way as described above.
- Duration of exposure (days)  
Duration of exposure will be calculated in days, using the following formula:  
(‘Date of Last Dose of Study Drug’\* - ‘Date of First Dose of Study Drug’\*\* ) + 1  
\* = Max(EX1ENDT, EX2ENDT, EX3ENDT) [Study Drug and Reference Drug Dosing-page of the CRF]  
\*\* = EX1STDT [Study Drug Dosing -page of the CRF]
- Overall treatment compliance (during overall treatment period)

In the study, the subjects will be instructed to take 2 tablets once per day, totaling a daily dose of study dose. Therefore, overall treatment compliance will be based on number of tablets and calculated as follows:

$$\text{Treatment compliance (\%)} = \frac{\text{[Total number of tablets actually received in the treatment period]}}{\text{[Total number of tablets planned to receive in the treatment period]}} \times 100$$

where total number of tablets planned to receive in the treatment period = 2 × number of days the subject was in the treatment period (the previous date of Week 52 visit [for completed subjects] / date of withdrawal date [for discontinued subjects] – date of initial dose of study drug +1), and total number of tablets actually received in the treatment period will be calculated as:

(total number of tablets dispensed) – (total number of tablets returned) – (total number of tablets lost).

- Treatment compliance during the 12 weeks of study (up to Weeks 12)  
Treatment compliance (%) =

$$\frac{\text{[Total number of tablets actually received up to Weeks 12]}}{\text{[Total number of tablets planned to receive up to Weeks 12]}} \times 100$$

where total number of tablets planned to receive up to Weeks 12 = 2 × number of days the subject was during 12 weeks (the previous date of Weeks 12 visit date [for completed Week 12 subjects] / date of withdrawal date [for discontinued before Week 12 subjects] – date of initial dose of study drug +1), and total number of tablets actually received up to Weeks 12 will be calculated as:

(total number of tablets dispensed up to Weeks 12) – (total number of tablets returned up to Weeks 12) – (total number of tablets lost up to Weeks 12).

- Treatment compliance during the 28 weeks of study (up to Weeks 28)  
Treatment compliance (%) =

$$\frac{[\text{Total number of tablets actually received up to Weeks 28}]}{\text{-----} \times 100} \\ [\text{Total number of tablets planned to receive up to Weeks 28}]$$

where total number of tablets planned to receive up to Weeks 28 = 2 × number of days the subject was during 28 weeks (the previous date of Weeks 28 visit date [for completed Week 28 subjects] / date of withdrawal date [for discontinued before Week 28 subjects] – date of initial dose of study drug +1), and total number of tablets actually received up to Weeks 28 will be calculated as:

(total number of tablets dispensed up to Weeks 28) – (total number of tablets returned up to Weeks 28) – (total number of tablets lost up to Weeks28).

\*If Weeks 28 visit date is missing but not discontinued before Day 197, then the total number of tablets planned to receive up to Weeks 28 = 2 × 196 (i.e. days from the previous date of scheduled visit at Week 28 – the date of initial dose of study drug + 1)

- Number of prior DMARD biologics, calculated as number of unique kinds of DMARD biologics prior to initial dose from following CRF page.  
[Concomitant Medication 2B -page of the CRF]  
[Biologic DMARD -page of the CRF]
- Number of prior DMARDs (including biologics), calculated as number of unique kinds of DMARD prior to initial dose from following CRF page.  
[Concomitant Medication 2B -page of the CRF]  
[Concomitant Medication(Non-Biologic DMARD) -page of the CRF]  
[Non Biologic DMARD\_MTX -page of the CRF]  
[Non Biologic DMARD except for MTX -page of the CRF]  
[Biologic DMARD -page of the CRF]
- MTX Dose at Baseline (mg/week) is defined as the dose which is taken during 6 days before “date of initial dose of study drug” up to “the initial dose of study drug”.

## 7 STATISTICAL METHODOLOGY

### 7.1 General Considerations

- For continuous variables, descriptive statistics will include the number of subjects (n), mean, standard deviation (SD), median, minimum, and maximum.
- For categorical variables: number and percentages of subjects will be described.
- For time-to-event variables: number and percentage of subjects with the event using Kaplan-Meier method, the cumulative event rate will be estimated and a plot will be constructed.
- All data processing, summarization, and analyses will be performed using SAS Drug Development (ver. 4.5), and PC-SAS (ver. 9.4) or higher versions.
- Specifications for table, figures, and data listing formats can be found in the TLF specifications for this study.

- For the definition of subgroups of interest can be referred to section [7.8](#)
- Summaries based on FAS and PPS (e.g. disposition, baseline and efficacy data) will be presented by actual treatment groups, unless specifically stated otherwise. Safety analysis and other summaries based on SAF will also be presented by actual treatment groups.
- Initial Randomization Set of efficacy analyses except for mTSS, erosion score, and joint space narrowing score are those of the efficacy data up to Week 12 and include the primary analysis (ACR20 at Week 12/ET) as described 7.4.1.1. This set will be analyzed by the initially treated groups (ASP015K 100 mg, ASP015K 150 mg, and Placebo) and statistical testing will be performed for ASP015K 100 mg, and 150 mg, compared with Placebo. In addition, statistical testing will also be conducted at Week 28/ET.

Table 3 Initial Randomization Set

Initial Randomization Arm Code	Initial Randomization Label	Analysis Scope
PLACEBO	Placebo	Screening, Week 0 to Week 12, Week 12/ET, Week 28/ET
100MG	100 mg	
150MG	150 mg	

- Treatment Sequence Set of efficacy analyses except mTSS, erosion score, and joint space narrowing score are those of the efficacy data up to Week 52. Taking into consideration a switch from placebo to active treatment at Week 12 or Week 28, this set will be analyzed by following groups defined below. The four types of "Placebo to ASP015K xx mg at Week xx" groups are not for primary objective and are conducted optionally for efficacy and safety.

Table 4 Treatment Sequence Set

Treatment Sequence Code	Treatment Sequence Label	Week0- Week12	Week 12- Week 28	Week 28- Week 52	Analysis Scope
SEQ1	100mg,	ASP015K 100 mg	ASP015K 100 mg	ASP015K 100 mg	Screening, Week 0 to Week 52, EOT
SEQ2	150mg	ASP015K 150 mg	ASP015K 150 mg	ASP015K 150 mg	
SEQ3	Placebo to 100mg at Week 12	Placebo	ASP015K 100 mg	ASP015K 100 mg	
SEQ4	Placebo to 150mg at Week 12	Placebo	ASP015K 150 mg	ASP015K 150 mg	
SEQ5	Placebo to 100mg at Week 28	Placebo	Placebo	ASP015K 100 mg	
SEQ6	Placebo to 150mg at Week 28	Placebo	Placebo	ASP015K 150 mg	

- 100 mg: subjects who initially treated ASP015K 100 mg
- 150 mg: subjects who initially treated ASP015K 150 mg

- Placebo to 100 mg at Week 12: subjects who initially treated Placebo group and switched 100 mg at Week 12 and at least one dose of ASP015K 100 mg drug after switched
  - Placebo to 150 mg at Week 12: subjects who initially treated Placebo group and switched ASP015K 150 mg at Week 12 and at least one dose of ASP015K 150 mg drug after switched
  - Placebo to 100 mg at Week 28: subjects who initially treated Placebo group and switched ASP015K 100 mg at Week 28 and at least one dose of ASP015K 100 mg drug after switched
  - Placebo to 150 mg at Week 28: subjects who initially treated Placebo group and switched ASP015K 150 mg at Week 28 and at least one dose of ASP015K 150 mg drug after switched
- 
- The analyses for mTSS (Appendix 1, Appendix 2), erosion score, and joint space narrowing score will be performed at Week 28/ET and Week 52/ET, and statistical testing will also be conducted at Week 28/ET, Week 52/ET, compared with Placebo. These analyses include primary analysis (mTSS change from baseline at Week 28/ET).
  - MedDRA 11.1 will be used as the coding dictionary for adverse event and medical history.
  - Statistical hypothesis testing will be performed only if specified. All statistical comparisons of treatment groups will be versus placebo (i.e., each ASP015K treatment versus placebo) and will be made using two sided tests at the 0.05 significance level, unless stated otherwise. Multiplicity adjustment will be done in the primary analysis and other analysis if specified.
  - Statistical analysis including hypothesis testing for efficacy variables to compare 100 mg or 150 mg versus Placebo, only the data for the pairwise comparison will be used.
  - All statistical results will be presented, as appropriate, by treatment group, by treatment group and scheduled visit; the schedule of assessments is provided in 7.11.4.
  - In addition, demographics and other baseline characteristics, and safety results will be provided for all ASP015K treatment groups combined ("ASP015K Total") and for all treatment groups, including placebo, combined ("Total"). Efficacy presentations will not contain combined treatment groups.
  - Chi-square test is continuity corrected in all analysis.
  - Confidence interval for binary outcome is continuity corrected in all analysis.
  - The values below the lower limit of quantitation (BQL) for  $\beta$ -D-glucan, hCG, Troponin, CK-MB will be treated as it is and these variables are not used for descriptive statistics and displayed in the listings. As for  $\beta$ -D-glucan, it is used for shift-from baseline analysis.
  - If anti-CCP antibody (U/mL) is beyond measurement (i.e.  $>500$  U/ml) then Anti-CCP antibody is regarded as 500 U/ml, and categorized in  $>500$  U/ml. Also, if anti-CCP antibody (U/mL) is below measurement (i.e.  $<0.6$  U/ml) then Anti-CCP antibody is regarded as 0.6 U/ml, and categorized in  $<4.5$  U/mL.

- CRP (mg/dL) is below measurement (i.e. <0.01 mg/dL) then CRP is regarded as 0.01 U/ml, and used for the calculation of DAS28-CRP, etc. and categorized in <1.0 mg/dL.
- If Rheumatoid Factor (IU/mL) is below measurement (i.e. <3 IU/mL), then Rheumatoid Factor is regarded as 3 IU/mL and categorized in <- 15 IU/ml.
- Baseline for safety is defined as last non-missing value before the first dose of study drug for all subjects including placebo assigned subjects.
- Baseline for efficacy is defined as value at Day1 before the first dose of study drug for all subjects including placebo assigned subjects.
- Change from baseline to post-baseline will be calculated as: post-baseline value - baseline value. If the baseline value is missing, then that subject is not included in the calculation at any visit.
- Percent change from baseline to post-baseline will be calculated as:  $100 \times (\text{change} / \text{baseline})$ . If the baseline value is 0 or missing, or post-baseline value is missing, then Percent change from baseline to post-baseline is missing.
- If onset date of AE is Unknown, then missing onset date of AE will be imputed as following steps.
  1. If only the day of the month is missing (e.g., 2013-03), then the first day of the month will be used (2013-03-01),
  2. If both day and month are missing (e.g., 2013), then the first day of January will be used (2013-01-01).
  3. If imputed onset date of AE is earlier than the first date of study drug, then the onset date of AE is onset at the first date of study drug, because AE data in CRF is collected only after the first date of study drug.

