7.4 Analysis of Efficacy

Efficacy analysis will be conducted on FAS and PPS. The interpretation of results from statistical tests will be based on the FAS. In the primary analysis of the primary variable, the purpose of using PPS is to assess the robustness of the results from the statistical tests based on FAS. Unless otherwise noted, analysis will be performed in the treatment groups at allocation (ASP015K 100 mg group, ASP015K 150 mg group, placebo group) and, if necessary, in the treatment groups taking into consideration a switch from placebo to active treatment (ASP015K 100 mg group, ASP015K 150 mg group, placebo–ASP015K 100 mg group at Week 12, placebo–ASP015K 150 mg group at Week 12, placebo–ASP015K 100 mg group at Week 28, placebo–ASP015K 150 mg group at Week 28).

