7.5 Analysis of Safety

The following analyses will be performed in SAF. Unless otherwise noted, analyses will be performed in the treatment groups at allocation (ASP015K 100 mg group, ASP015K 150 mg group, placebo group) and, when necessary, in the treatment groups after placebo was switched to active treatment (ASP015K 100 mg group, ASP015K 150 mg group, placebo–ASP015 100 mg group at Week 12, placebo–ASP015K 150 mg group at Week 12, placebo–ASP015K 100 mg group at Week 28, and placebo–ASP015K 150 mg group at Week 28).

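### SAP 7.1 makes actual treatment groups the default for FAS and PPS summaries, against the protocol's groups at allocation, and the SAP does not say that the mTSS tests use the randomised arm

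*SAP*

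**What the plan says.** Protocol 7.4, on efficacy in the FAS and PPS: "Unless otherwise noted, analysis will be performed in the treatment groups at allocation". It names the three arms and also allows analysis, "if necessary, in the treatment groups taking into consideration a switch from placebo to active treatment". Nothing there exempts mTSS.

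SAP 7.1 sets another default: "Summaries based on FAS and PPS (e.g. disposition, baseline and efficacy data) will be presented by actual treatment groups, unless specifically stated otherwise". It names efficacy data and gives no reason for leaving the protocol's rule. The sentence after it applies the same grouping to the SAF.

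The SAP then makes exceptions. One bullet in 7.1 defines the "Initial Randomization Set of efficacy analyses except for mTSS, erosion score, and joint space narrowing score", and SAP 7.4 places efficacy up to Week 12, with the ACR20 primary analysis, in that set. Table 3 labels its arms under "Initial Randomization Arm Code", but the text says: "This set will be analyzed by the initially treated groups (ASP015K 100 mg, ASP015K 150 mg, and Placebo". The Treatment Sequence Set also leaves out the three radiographic scores.

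For those scores, the SAP 7.1 bullet gives time points and the comparator. SAP 7.4.1.1 and Appendix 1 (footnote 2) give a treatment factor with three labels. None says whether a patient is placed by randomisation or by drug received.

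**The concern.** Steps 1 to 4 of the closed testing procedure are the confirmatory evidence. A comparison of randomised arms keeps each patient in the arm assigned, whatever was dispensed. The SAP's general default, read literally, could move a wrongly dispensed patient to the arm of the drug taken. For ACR20 the Initial Randomization Set largely removes that risk, subject to the loose phrase about initial treatment. For mTSS the exception does not apply, so within the SAP the only general grouping rule is the one that names actual treatment. If such a patient turned up, the team would have two documents giving different answers for a confirmatory test.

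**Working it through.** **The plan's own figure.** SAP section 4 assumes mTSS changes of 2.0 (placebo) and 0.5 (150 mg), SD 4.0, two-sided 5% and 90% power. Then n = 2 × (1.960 + 1.282)² × 4.0² / 1.5² = 149.4, or 150 per group. With the exact t distribution, power is 0.899 at 150 and 0.901 at 151, so the stated 151 is reproduced. Allowing 10% drop-out, 151 / 0.9 = 167.8, or 168, and the planned 170 covers it. The grouping rule does not enter this calculation.

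**The passages side by side.**
- *ACR20 (Steps 1 and 2).* The protocol gives allocation. The SAP gives the Initial Randomization Set with randomisation codes, described as initially treated groups. In the Table 4 definitions, initially treated can simply mean before the planned switch.
- *mTSS (Steps 3 and 4).* The protocol gives allocation. The SAP gives three labels and no basis, with a default elsewhere of actual treatment.
- *Planned switchers.* SAP 7.11.1 extrapolates a Week 12 switcher's mTSS from values before the switch. SAP 7.11.4 likewise uses the last pre-switch observation for non-radiographic visits. They stay with placebo in the primary tests.
- *Terms.* The mTSS text of SAP 7.11.1 describes the placebo arm once by initial treatment and once by initial randomisation.

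The two rules therefore part only for a patient whose first study drug differed from allocation. The documents give no rate for this. I assume 0 to 5 such patients, with 170 per arm.

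**ACR20.** The planned rates are 25%, 54.5% and 65.5%. Move one placebo responder to 150 mg: (111.35 + 1)/171 − (42.5 − 1)/169 = 0.4115, against 0.405, a shift of 0.65 points. Over responders and non-responders moved in either direction, the shift is 0.53 to 0.65 points for 150 mg and 0.47 to 0.71 for 100 mg. In whole patients, with five active responders all moved to placebo:
- 150 mg: 111/170 v 42/170 (40.6 points, Fisher p = 5.4e-14) becomes 106/165 v 47/175 (37.4 points, p = 3.8e-12).
- 100 mg: 93/170 v 42/170 (30.0 points, p = 2.2e-8) becomes 88/165 v 47/175 (26.5 points, p = 9.0e-7).

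**mTSS, Step 3, on the mean scale.** Moving a placebo patient with change y to 150 mg shifts the difference by (2.0 − y)/169 − (y − 0.5)/171. This is +0.009 at y = 0.5, −0.009 at y = 2, −0.056 at y = 6 and −0.103 at y = 10. The standard error is 4.0 × √(2/170) = 0.434.

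**mTSS, Step 3, by rank ANCOVA.** I used 1,500 simulated trials with normal changes and a lognormal baseline independent of change; these shapes are assumptions. Mean |t| was 3.38 and power 91.4%. Moving one random placebo patient to 150 mg shifted t by −0.18 to +0.19 (95% range) and changed significance in 1.5% of trials. Moving the placebo patient with most progression shifted t by about 0.20 and changed significance in 3.1%.

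**Cost of staying with the randomised arm.** If 0, 1, 2 or 5 patients per arm took the other arm's drug throughout, the Step 3 difference is 1.5 × (1 − 2m/170), with m the number per arm. Power by t-test at 170 per arm is 0.932, 0.926, 0.920 or 0.901.

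Step 4 cannot be sized, because the documents give no planned 100 mg mTSS change.

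**The case against.** The best defence is that the SAP 7.1 sentence concerns how summaries are presented, yields wherever something else is stated, and does not expressly set the factor in a test. SAP section 1 presents the SAP as an elaboration of the protocol's analysis, so its silence on mTSS need not displace protocol 7.4. The SAP uses its own exceptions freely: ACR20 goes to the Initial Randomization Set, and so does disposition, which the default names as an example. SAP 7.11.1 uses the treated and randomised terms for the same patients, which suggests that the authors saw no difference. Drug numbers are assigned under blind conditions by the registration center, and no dispensing error is reported.

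Most of this stands. It shows that the intention was probably the randomised arm, and it limits the consequence. It does not remove the conflict, because the default names efficacy data and no SAP sentence exempts mTSS from it.

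A reader might go further in two ways. One is to say that the randomised basis for mTSS is stated nowhere. That is wrong across the two documents, since protocol 7.4 covers every efficacy analysis. The other is to say that placebo patients who switch at Week 12 would leave the placebo arm. If 20%, 40% or 60% did (assumed rates), 136, 102 or 68 placebo patients would remain and power against 170 on 150 mg would be 0.90, 0.85 or 0.74. The imputation rule in SAP 7.11.1 does not support that reading.

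**Conclusion.** The conflict is real and minor. The SAP's default departs from the protocol's without explanation, and the SAP does not state the randomised basis for Steps 3 and 4. Results change only if a patient's first study drug differed from allocation; with no such patient they are identical. At the planned ACR20 rates, Steps 1 and 2 hold even with five responders moved. Step 3 has a small sensitivity, and its percentages are conditional on one patient being moved under the assumed distributions, so they are not estimates of risk to this trial. On the PPS, such a patient may already be excluded for a major protocol violation. The sample size and every other stated figure are unaffected.

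**What to change.** In SAP 7.1 and 7.4.1.1, state that Steps 1 to 4 and all three-arm efficacy comparisons on the FAS and PPS, including mTSS, erosion score and joint space narrowing score, use the arm assigned at randomisation, as in protocol 7.4. Remove the FAS and PPS from the actual-treatment default. For the efficacy use of the Initial Randomization Set, replace *initially treated groups* with *initially randomised groups*. In SAP 7.11.1, use *initially randomised to placebo* throughout. Treatment Sequence Set summaries keep the Table 4 groups.

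Add no new rule for the SAF here. Protocol 7.5 says "Unless otherwise noted, analyses will be performed in the treatment groups at allocation". SAP 7.1 says "Safety analysis and other summaries based on SAF will also be presented by actual treatment groups". SAP 7.5 runs safety analyses up to Week 12 on the Initial Randomization Set, and SAP 7.2.1 tests withdrawal for lack of efficacy on the SAF by that same set. These need reconciling separately.

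The cost is SAP wording only. No test, sample size or data collection changes.
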